2.3. Summary of Findings from Previous Clinical Studies

2.4. Rationale for the Clinical Study

2.5. Risk-benefit Assessment

Current antipsychotics used in patients with schizophrenia although effective are not perfect as they might be associated with different side effects. The development of new, effective therapy with improved safety profile would be a beneficial treatment options for schizophrenia patients. The PDE10 inhibitors, based on several preclinical models, may represent a new approach for treatment of psychosis. The use of treatment with new mechanism of action may exert some risks, which, based on available information, was recognized and the study was design to minimize it.

In a similar phase 2, randomized, placebo-controlled study, the efficacy and safety of a selective PDE10A inhibitor (TAK-063) in patients with an acute exacerbation of schizophrenia were evaluated [25]. In this study, no clinically relevant or consistent differences were observed between study drug and placebo groups for hematologic, renal, or hepatic lab test results, vital signs, or ECG. Most subjects reported AEs that were mild or moderate in severity, and the AEs reported in this study were generally consistent with the previously conducted phase 1 studies [26, 27]. AEs experienced by ≥5% of subjects in the IMP (TAK-063) group were akathisia (placebo: 4.9%; IMP: 13.3%), somnolence (placebo: 2.5%; IMP: 12.0%), dyspepsia (placebo: 7.4%; IMP: 10.8%), headache (placebo: 11.1%; IMP: 7.2%), nausea (placebo: 6.2%; IMP: 6.0%), dystonia (placebo: 1.2%; IMP: 6.0%), and decreased appetite (placebo: 1.2%; IMP: 6.0%). None of the serious adverse event (SAE) was considered related to study drug. The investigated PDE10A inhibitor did not result in any deaths, and most AEs were mild or moderate in severity and did not result in the specific study discontinuation [26, 27].

Phase I study results in healthy volunteers showed that CPL500036 compound is generally safe and well tolerated. Potential risks associated with use of CPL500036 based on most frequently AE occurrence in phase I study, assessed as related or possible related with IMP:

- Drowsiness/somnolence,
- Feeling calm,
- Headache,
- Sensation of cold,
- Sensation of hot/heat.

The intensity of observed AEs was classified as mild or moderate. All the AEs were transient and their frequency decreased after Day 3 of administration (in multiple dosing). The most

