The 02PDE2019 study is considered a short term study with up to 7 days of medication washout period and 28-day treatment phase. The CPL500036 compound will be used in monotherapy, so other antipsychotic treatments will be discontinued, what is in line with the EMA guidelines which states that "treatments that may augment the test treatment should be excluded, despite the consequences of these exclusions for generalizability of the trial results. Therefore other antipsychotic drugs should be discontinued (...)" [30]. The protocol has been designed to minimize the risk to all research participants. This study will be performed in controlled settings, all patients will be hospitalized to assure patients safety. Subjects will be monitored to detect AEs during the study and followed appropriately to ensure resolution of AEs.

To manage potential side effects and symptoms that may occur, allowed treatments are described. During the study lorazepam may be administered for anxiety/agitation or to aid sleep. To manage insomnia from z-drugs, use of zolpidem is allowed in the study. To treat extrapyramidal side effects and akathisia benzatropine/biperiden and propanolol are permitted, respectively. The daily and weekly limits of those medications that can be used, on a PRN (as needed) basis are provided (rules for medication administration in Section 5.4.3). If a patient's condition will require to exceed the specified dose, it must be recorded as Serious Adverse Event.

During the whole study all the patients will be closely observed by the Investigator or appointed staff members to assure maximal safety. Safety is to be ensured by performing clinical assessments/ evaluations and clinical laboratory measurements/ evaluations. This includes i.a. monitoring of vital signs with 3-positional blood pressure and pulse measurements, ECG measurements and extrapyramidal side effects monitoring using Extrapyramidal Symptom Rating Scale (ESRS) assessments. Patients at imminent risk of suicide or injury to self, others, or property or participants who within the past year prior to screening have attempted suicide will be excluded from the study and risk of potential suicide ideations occurrence will be assessed during the study.

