During the study lorazepam may be administered for anxiety/agitation or to aid sleep; from other medications to manage insomnia, known as z-drugs, zolpidem is preferred and allowed. Lorazepam and zolpidem are not to be used in close temporal proximity (administration within 4h of each other). In addition, benzatropine/biperiden may be administered for treatment of extrapyramidal side effects and propranolol may be administered for treatment of akathisia. Lorazepam, zolpidem, benzatropine/biperiden and propranolol are allowed according to the instructions outlined in Table 5 below. Within the daily and weekly limits shown in Table 5, lorazepam, zolpidem, benzatropine/biperiden, and propranolol are permitted upon the Investigator or designee decision and are allowed on a PRN (as needed) basis.

If the patient's condition will require administration of higher dose of lorazepam, zolpidem, benzatropine/biperiden, or propranolol (exceeding the limits given in Table 5), it must be recorded as Serious Adverse Event (SAE).

The adverse event (AE) associated with the need for lorazepam, zolpidem, benzatropine/biperiden, or propranolol should be recorded on the AE eCRF. The amount and timing of each lorazepam, zolpidem, benzatropine/biperiden, or propranolol administration should be recorded for each patient in the eCRF.

Table 5 Restrictions on the Use of Lorazepam, Zolpidem, Benzatropine/Biperiden, and Propranolol during the Study

Medication	Study Period	Dosage Allowed	Timing Restrictions
Lorazepam	Screening Period and Treatment Period to Day 28, inclusive	Maximum of 6 mg/day AND	Not within 8 hours prior to PANSS, CGI-S, CGI-I or C-SSRS, BACS Not within 4 h of zolpidem administration
		Maximum 6 times/week (at least 1 day break between weeks)	
	Follow up period – Since Day 29 and onwards	According to SmPC	
Zolpidem	Screening Period and Treatment Period to Day 28, inclusive	Maximum of 10 mg/day	Not within 8 hours prior to PANSS, CGI-S, CGI-I or C-SSRS, BACS Not within 4 h of lorazepam administration
		Maximum 4 times/week	
	Follow up period – Since Day 29 and onwards	According to SmPC	
Benzatropine	Screening Period to Day 28, inclusive	Maximum of 4 mg/day	Not within 8 hours of BACS, ESRS
Biperiden		According to SmPC	
Propranolol	Screening Period to Day 28, inclusive	Maximum of 40 mg/day	

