8.3.1.1. Definitions

8.3.1.1.1. Definition of Adverse Event

Any untoward medical occurrence in a subject administered an IMP and which does not necessarily have a causal relationship with this treatment. An adverse event (AE) can therefore be any unfavourable and unintended sign (including an abnormal laboratory finding), symptom, or disease temporally associated with the use of a medicinal (investigational) product, whether or not related to the medicinal (investigational) product.

Other untoward events occurring in the framework of a clinical study will be recorded as AEs, e.g. those occurring during treatment-free periods (including Screening or post-treatment follow-up periods), in association with study-related procedures and assessments, or under placebo. For study drugs, lack of efficacy may be an expected potential outcome and should not be reported as an AE unless the event is unusual in some way, e.g., greater in severity.

Concomitant illnesses, which existed prior to entry into the clinical study, will not be considered AEs unless they worsen during the Treatment Period. Pre-existing conditions will be recorded as part of the subject's medical history.

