8.3.1.1.2. Definition of Serious Adverse Event

A SAE is defined as any untoward medical occurrence that at any dose:

- Results in death,
- Is life-threatening; this means that the subject was at risk of death at the time of the event; it does not mean that the event hypothetically might have caused death if it were more severe,
- Requires in-patient hospitalization or prolongation in existing hospitalization,
- Results in persistent or significant disability/incapacity or substantial disruption of the ability to conduct normal life functions,
- Is a congenital anomaly/birth defect, or
- Is another important medical event (see below).

Important medical events that do not result in death, are not life-threatening or do not require hospitalization may be considered SAEs when, based on appropriate medical judgment, they may jeopardize the subject and may require medical or surgical intervention to prevent one of the outcomes listed above. Examples of such medical events include allergic bronchospasm requiring intensive treatment in an emergency room or in a physician's office, blood dyscrasias or seizures

that do not result in in-patient hospitalization, and the development of drug dependency or drug abuse.

A distinction should be drawn between serious and severe AEs. Severity is a measure of intensity whereas seriousness is defined by the criteria above. For example, a mild degree of gastrointestinal bleeding requiring an overnight hospitalization for monitoring purposes would be considered a SAE but is not necessarily severe. Similarly, an AE that is severe in intensity is not necessarily a SAE. For example, alopecia may be assessed as severe in intensity but would not be considered a SAE.

Medical and scientific judgment should be exercised in deciding if an AE is serious and if expedited reporting is appropriate.

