8.3.1.4. Reporting of Serious Adverse Events

The Investigator will review each SAE and evaluate the intensity and the causal relationship of the event to study drug. All SAEs will be recorded from signing of the ICF until the final Follow-up Visit. Serious AEs occurring after the final Follow-up Visit and coming to the attention of the Investigator must be reported only if there is (in the opinion of the Investigator) reasonable causal relationship with the study drug.

The Investigator is responsible for providing notification to the Sponsor of any SAE, whether deemed IMP-related or not, that a subject experiences during their participation in study within 24 hours of becoming aware of the event.

As a minimum requirement, the initial notification should provide the following information:

- Study number,
- Patient number,
- Sex,
- Date of birth,
- Name of Investigator and full clinical site address,
- Details of SAE,
- Criterion for classification as 'serious',
- Study drug name, or code if unblinded, and treatment start date,
- Date of SAE onset,
- Causality assessment (if sufficient information is available to make this classification).

The Sponsor will request clarification of omitted or discrepant information from the initial notification. The Investigator or an authorized delegate is responsible for sending via email the requested information to the Sponsor within 24 hours of the Sponsor's request.

Initial reports of SAEs must be followed later with detailed descriptions, including clear photocopies of other documents as necessary (e.g. hospital reports, consultant reports, autopsy reports), with the subject's personal identifiers removed. All relevant information obtained by the Investigator through review of these documents will be recorded and emailed to the Sponsor within 24 hours of receipt of the information. If a new SAE report form is emailed, then the Investigator must sign and date the form. The Sponsor may also request additional information on the SAE, which the Investigator or an authorized delegate must send via email to the Sponsor within 24 hours of the request.

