4.8.1. Adverse event analysis

Any undesirable signs, symptoms or medical conditions occurring or worsening of pre-existing conditions between signing informed consent and the first administration of the study medication are considered as pre-treatment AEs. Undesirable signs, symptoms or medical conditions or worsening of pre-existing conditions occurring after the first administration of study medication are considered as treatment emergent adverse events (TEAEs).

A TEAE will be analyzed as related to study medication (i.e. as adverse drug reaction, ADR) if the relationship to study treatment was documented as 'unlikely', 'possible', 'probable', or 'definite' or if the relationship to study treatment is missing.

An overview table presenting the incidence of the following AE categories will be presented. Percentage of patients in each category will be compared between treatments as a difference in proportions between treatments including a 95% CI based on the Agresti – Caffo method (2000):

- All AEs
- Pre-treatment AEs
- Serious AEs (SAEs) (including pre-treatment SAEs)
- Treatment emergent AEs (TEAEs)
- Treatment emergent SAEs (TESAEs)
- Severe TEAEs
- Related TEAEs
- Related severe TEAEs
- TEAEs leading to reduction of dose
- TEAEs leading to interruption of dose
- TEAEs leading to permanent discontinuation (i.e. withdrawal) of study medication
- Related TEAEs leading to permanent discontinuation of study medication
- AEs leading to death (i.e. outcome of AE is fatal)
- TEAEs leading to death
- Related TEAEs leading to death

All treatment emergent AEs (TEAEs) and all serious TEAEs will be tabulated by MedDRA SOC and PT presenting the number and percentage of patients reporting the AE and the number of AEs reported. Additional tables will distinguish the events by whether the AE was related to study medication and by maximum severity.

All AEs documented in the eCRF will be listed by patient. Data listings will include patient ID, treatment group, verbatim term, preferred term, system organ class, start and stop date and relative day of the AE, severity, medications (yes/no), seriousness, action taken with study medication, relationship to study medication, and outcome will be provided. TEAEs will be flagged as such. In addition, separate listings for all SAE's, deaths and AEs leading to discontinuation (action taken with study treatment = drug withdrawn, or AE is reason for early termination) will be presented.

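### SAP 4.8.1 compares SAE and TESAE proportions between arms with no row that separates records made serious only by the rescue-limit rule in Protocol 5.4.3

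*Protocol*

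**What the plan says.** Protocol 5.4.3 sets limits in Table 5 for lorazepam, zolpidem, benzatropine, biperiden and propranolol. If a patient needs a higher dose, "it must be recorded as Serious Adverse Event (SAE". The risk-benefit section (2.5) repeats the rule: where the condition "will require to exceed the specified dose, it must be recorded as Serious Adverse Event". Neither place attaches a clinical criterion.

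The SAE definition in 8.3.1.1.2 has the usual criteria and a judgment-based one, "Is another important medical event (see below". Over-limit rescue is not among them. Section 8.3.1.1.1 says that "lack of efficacy may be an expected potential outcome and should not be reported as an AE", with an exception for events that are unusual, for example in severity.

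On analysis, SAP 4.8.1 states: "Percentage of patients in each category will be compared between treatments as a difference in proportions between treatments", with Agresti-Caffo 95% intervals. All SAEs (pre-treatment included) and TESAEs are two of the categories. Serious TEAEs are also tabulated by SOC and preferred term, with further tables by relatedness and maximum severity. The AE listing carries a yes/no field for medication and a field for seriousness, but neither the seriousness criterion nor a rescue dose.

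The data for a split will exist. Protocol 5.4.3 says "The amount and timing of each lorazepam, zolpidem, benzatropine/biperiden, or propranolol administration should be recorded for each patient in the eCRF", and the SAE notification in 8.3.1.4 asks for the "Criterion for classification as" serious.

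**The concern.** The trial has two routes to an SAE: a clinical one and a dosing trigger. The dosing trigger may depend on treatment. Lorazepam and zolpidem treat agitation and sleeplessness, which may be more common on placebo. Biperiden, benzatropine and propranolol treat extrapyramidal effects and akathisia, which may be more common on drug. In the similar PDE10A-inhibitor trial described in Protocol 2.5, the figures were "akathisia (placebo: 4.9%; IMP: 13.3" percent.

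Over-limit lorazepam for agitation can reflect lack of efficacy, which the AE definition normally keeps out of AE reporting. The TESAE difference can therefore be diluted by records common to both arms, or shifted by something other than harm. The two sources can also pull in opposite directions. At stake is how clearly the main serious-event comparison can be read. The primary endpoint is not affected.

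**Working it through.** **Text check.** The rule stands in the current text of 5.4.3 and 2.5. No category, flag, sensitivity summary or listing field in SAP 4.8.1 identifies why a record is serious. SAP 4.5 summarises concomitant medication by ATC level only, with no link to Table 5. Rescue limits also apply during screening and washout, but over-limit use then enters only the all-SAE row, because TEAEs start after the first dose.

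**Arm size.** SAP 2.4 plans 50 evaluable patients per group for 80% power at effect size 0.5, two-sided 10%. This reproduces: n = 2(1.645 + 0.842)²/0.5² = 49.5, so 50. The 55 randomized per arm equals 50 × 1.1. The figure is not in dispute and only supplies the denominator. One patient is 1/55 = 1.8 points.

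**Interval.** Agresti-Caffo: p = (x + 1)/(n + 2) in each arm, then (p1 − p2) ± 1.96 √[p1(1 − p1)/(n + 2) + p2(1 − p2)/(n + 2)]. For 2 against 1: p1 = 3/57 = 0.0526, p2 = 2/57 = 0.0351, difference 0.0175, SE 0.0383, giving −5.8 to 9.3 points.

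**Illustrations.** Every count below is an assumption, because the documents give no SAE or over-limit rates. Each pair is one dose arm, then placebo, with 55 patients each. Each patient is taken to have only one kind of TESAE; overlap would reduce the shift. The difference shown is the raw one, in percentage points.

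| Other TESAEs | 5.4.3-only | Total | Difference | 95% CI |
|---|---|---|---|---|
| 2, 1 | 0, 0 | 2 v 1 | +1.8 | −5.8 to 9.3 |
| 2, 1 | 4, 4 | 6 v 5 | +1.8 | −9.9 to 13.4 |
| 2, 1 | 2, 6 | 4 v 7 | −5.5 | −16.9 to 6.4 |
| 0, 0 | 4, 0 | 4 v 0 | +7.3 | −1.1 to 15.1 |
| 0, 0 | 5, 0 | 5 v 0 | +9.1 | 0.1 to 17.4 |
| 2, 2 | 6, 0 | 8 v 2 | +10.9 | −0.6 to 21.6 |
| 2, 2 | 7, 0 | 9 v 2 | +12.7 | 0.8 to 23.7 |
| 2, 2 | 1, 8 | 3 v 10 | −12.7 | −24.5 to −0.1 |

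Row 2 shows dilution: the same estimate, but the interval widens from 15.0 to 23.3 points. Row 3 shows a change of sign, with the interval still including zero. The remaining rows show when these records alone would make the interval exclude zero: 5 against 0 with no other TESAEs, or an excess of 7 when each arm has 2 others.

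**The case against.** The plan is consistent with itself: it counts as SAEs what the protocol says to record as SAEs, and a sponsor may set a trial-specific trigger. Safety is descriptive, and no hypothesis or decision rule rests on the TESAE interval. That stands, and it is why this is an improvement and not an error.

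Some over-limit cases will be serious in their own right. Agitation needing more than 6 mg/day of lorazepam may be an important medical event, or may fit the severity exception in 8.3.1.1.1. This also stands. A reader might infer that every such record is a non-event or that 5.4.3 overrides the AE definition; the documents support neither.

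The records are also not hidden. Protocol 10.9 lists concomitant medication by subject with dose, frequency and indication, SAP 4.5 confirms such listings, and 4.8.1 plans a separate SAE listing. With few SAEs, cases could be matched by hand. That weakens the point, but case matching after unblinding does not replace a pre-specified summary.

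The akathisia figures concern another compound at any severity, and most adverse events in that trial were mild or moderate. They show why rescue need might differ by arm, not how often 40 mg/day of propranolol would be exceeded.

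**Conclusion.** The point holds as a modest one. Followed exactly, the plan yields SAE and TESAE differences that mix clinically serious events with a dosing trigger that may depend on treatment, and no planned summary shows the difference without the latter.

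The scale is 1.8 points per affected patient at 55 per arm, provided the patient has no other TESAE. Direction and total size cannot be derived from the documents. A reader might infer that the comparison will produce a false safety signal, or that it is biased in a known direction. The documents do not support either reading: they contain no rates, the two kinds of rescue may act in opposite directions, and the interval excludes zero through these records alone only under lopsided splits. The realistic risk is a diluted or shifted estimate.

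It is also unclear whether exceeding only a weekly-frequency limit triggers the rule, since 5.4.3 speaks both of a higher dose and of the Table 5 limits.

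**What to change.** Keep the 5.4.3 reporting rule. Before the Day 28 unblinding, add a mechanical rule to SAP 4.8.1:

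- Flag an SAE as 5.4.3-only when eCRF rescue dose and timing exceed Table 5 and the SAE notification shows no other seriousness criterion. An entry of important medical event should not count as another criterion unless a separate medical reason is given, because it may be entered by default.
- State whether a weekly-frequency excess counts, and whether an excess over the SmPC limits that Table 5 sets for lorazepam and zolpidem from Day 29 counts.
- Apply the rule at the planned blind data review to data up to Day 28. Under SAP 3.6 the safety analysis follows that unblinding, so some follow-up SAEs will arrive later. Apply the same rule to them unchanged, ideally by someone blinded to arm.
- Show the TESAE and SAE rows with and without flagged records, and tabulate over-limit rescue by drug and arm so that an extrapyramidal or akathisia signal stays visible.

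The cost is a small reconciliation of rescue data, SAE notifications and AE data, a few table rows, and some judgment in classification. No protocol change or new data collection is needed.

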5.4.3. Prior and Concomitant Treatments

Medication restrictions applicable before dosing are described in Section 5.3 (exclusion criteria). Prior medication will be recorded.

Any medicinal product, prescribed or over-the-counter (OTC), taken by a subject other than the IMP, is considered concomitant medication. Permitted medication (for prolonged use) includes only paracetamol in recommended doses (≤ 2 g per day) after approval by the Investigator or designee. Higher doses of paracetamol, up to 4 g per day may be given at the discretion of the

Investigator or designee to treat AEs such as fever and headache (only for short terms issues). Any concomitant treatment will be given only if deemed strictly necessary by the Investigator or designee. Use of concomitant medication will be recorded and reported.

Allowed concomitant medications taken by the patient in fasting conditions can be taken consistently with the current recommendations, but at least 1 hour interval between concomitant medication and IMP administration must be maintained with IMP taken as first.

Starting on the first day of Screening Period and as applicable, all antipsychotic or other psychotropic medications will be stopped with clinically appropriate titration down as per Investigator clinical judgment. Thereafter, patients will be instructed not to take any medications during the conduct of the study unless approved by the Investigator. Any patient who is unable to be safely discontinued from current antipsychotic therapy or other psychotropic medications will not be eligible for the study (see Section 7).

Medication history (psychotropic medication history during the previous 5 years and all other medications during the past 12 months) will be recorded at Screening (Visit 1) in the eCRF. Thereafter, any changes in concomitant medications or new medications added will be recorded in the eCRF.

Patients will not be eligible for the study if they have used any depot antipsychotic within 1 month (30 days) prior to Screening. The using of mianserin, mirtazapine, nefazadone, cyproheptadine, or fluvoxamine within 1 month (30 days) before Screening is not recommended.

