11.7. Protocol Approval and Amendment(s)

Before the start of the clinical study, the CSP and other relevant documents will be approved by the IRB/IEC, in accordance with local legal requirements. The Sponsor must ensure that all ethical and legal requirements have been met before the first subject is enrolled in the clinical study.

This protocol is to be followed exactly. To alter the protocol, amendments must be written, which must be released by the responsible staff and receive IRB/IEC approval prior to implementation (as appropriate).

Administrative changes may be made without the need for a formal amendment but will also be mentioned in the integrated CSR. All amendments will be distributed to all study protocol recipients, with appropriate instructions.

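### Table 5 bars benzatropine within 8 hours *of* BACS and ESRS rather than *prior to* them; read literally, this also blocks it for about 8 h after each ESRS and protects neither scale (minor wording fix)

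*Protocol*

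**What the plan says.** Protocol section 5.4.3 permits four rescue drugs and makes Table 5 the governing rule: "Lorazepam, zolpidem, benzatropine/biperiden and propranolol are allowed according to the instructions outlined in Table 5 below". Benzatropine and biperiden are for extrapyramidal side effects, and propranolol is for akathisia. Within the table's daily and weekly limits, these drugs "are permitted upon the Investigator or designee decision and are allowed on a PRN (as needed) basis".

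The Timing Restrictions column of Table 5 uses two forms of words:

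- Lorazepam and zolpidem, relative to ratings: "Not within 8 hours prior to PANSS, CGI-S, CGI-I or C-SSRS, BACS".
- Lorazepam, relative to zolpidem: "Not within 4 h of zolpidem administration", with a mirror entry in the zolpidem row.
- Benzatropine, relative to ratings: "Not within 8 hours of BACS, ESRS".

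The benzatropine row applies from Screening through Day 28. Table 9 and section 2.5 only refer back to section 5.4.3. Section 11.7 adds, in general terms, "This protocol is to be followed exactly".

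**The concern.** The ESRS is the scale the protocol uses to monitor extrapyramidal effects, and benzatropine is a named treatment for them. A limit before the rating makes sense, because a recent anticholinergic dose could mask signs on the ESRS or affect cognition on the BACS. A limit after the rating has no such purpose for either scale, yet it falls in the hours after symptoms have been seen.

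Sites could read the cell differently. One might delay a benzatropine dose by some hours. Another might give it and log a timing deviation. A third might give it and log nothing. What is at stake is prompt treatment and uniform handling of deviations.

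**Working it through.** The plan gives no figure of its own on this point, so the check is a timeline.

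**Inputs**
- On-treatment ESRS: Days 1, 7, 14, 21 and 28, starting about 2 h post-dose and after BACS where BACS is done (Protocol 8.3.7).
- BACS: Day -1, Day 14 and Day 28 (Protocol 8.5.4).
- Treatment Period: 28 × 24 = 672 h.
- Dystonia in the cited trial of another PDE10A inhibitor: 6.0% on drug, 1.2% on placebo (Protocol 2.5).
- 55 patients per group (Protocol 10.16).

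**1. Length of the bar on an ESRS day** (rating duration ignored)
- *Prior to*: from 2 − 8 = −6 h to +2 h relative to dose, which is 8 h.
- *Of*, read both ways: from −6 h to 2 + 8 = +10 h, which is 16 h.
- Extra bar: 8 h per rating, from about 2 to 10 h post-dose.

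**2. Total on treatment.** 5 × 8 = 40 h; 40/672 = 6.0%.

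**3. Does the extra half protect a BACS or ESRS rating?**
- A dose given after a rating cannot alter that rating.
- The next on-treatment ESRS is 6 × 24 = 144 h later (Day 1 to Day 7) or 7 × 24 = 168 h later. The extra bar therefore ends 144 − 16 = 128 h or 168 − 16 = 152 h before the next pre-rating window opens.
- Before treatment the gaps are shorter: about 48 h from Day -1 to Day 1, and about 24 h if screening is on Day -2, assuming similar clock times. The margins are still 32 h and 8 h.
- A dose between BACS and ESRS in one session is already barred by *prior to*, because ESRS comes second.
- After the Day 28 rating no later rating falls within the period the row covers.

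So the extra half protects no rating on either named scale.

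**4. Could it be meant for another same-day assessment?** Several follow the ESRS:
- C-SSRS on Days 14 and 28.
- Neurological examination, from 5 h post-dose, on Days 7, 14, 21 and 28.
- Physical, ophthalmological and dermatological examinations, from 5 h post-dose, on Day 28.
- PK samples at 4 h and 8 h on Days 1 and 7, in both sampling groups.
- Vital signs at 9 h on Days 1 to 7, 14, 21 and 28.

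The cell names none of these, although the lorazepam and zolpidem rows do name C-SSRS. None has the same days as the bar: the neurological examination is not done on Day 1, and the 9 h vital signs are also taken on Days 2 to 6, when no ESRS is rated and so no bar applies.

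**5. How many patients?** Using dystonia only: 55 × 0.060 = 3.3 per active arm and 55 × 0.012 = 0.66 on placebo.

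| Assumed onset | Per active arm | Placebo | Whole trial |
|---|---|---|---|
| Uniform over 28 days | 3.3 × 40/672 = 0.20 | 0.66 × 40/672 = 0.04 | 2 × 0.196 + 0.039 = 0.43 |
| Always 2 to 10 h post-dose, even over days | 3.3 × 5/28 = 0.59 | 0.66 × 5/28 = 0.12 | 2 × 0.589 + 0.118 = 1.30 |

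The ceiling, with every onset inside the window, is 3.3 per active arm.

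**The case against.** The strongest reply is that this is a copy-edit. A completed rating cannot be changed by a later dose, so a sensible investigator will read *of* as *prior to*, and harm requires someone to choose the pointless reading. The sentence in section 11.7 about following the protocol concerns approval and amendments, and is weak support for a literal reading of one preposition. Section 5.4.3 also leaves treatment to clinical judgement: "Any concomitant treatment will be given only if deemed strictly necessary by the Investigator or designee".

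Much of this stands. The intent was probably one-way, and section 11.7 carries little weight. But the two-way reading is not contrived. The same column uses *of* for the lorazepam–zolpidem interval, and the body text makes that interval apply in either order. The permission to use the drugs as needed does not lift the timing rule, because the section separately ties use to Table 5. A rule applied at multiple clinical units should not depend on each one guessing the intent.

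A second reply is that other treatment remains available. Propranolol is not touched, and it covers akathisia, the most frequent event on drug in the cited trial (13.3%). Biperiden may be free of the limit too, but its timing cell cannot be read from the extracted table and may be merged with benzatropine's. If biperiden is unrestricted, most of the safety concern disappears. If the cells are merged, the ambiguity covers both drugs.

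**Conclusion.** The wording is ambiguous. Its literal reading withholds a named treatment for about 8 h after the rating that would detect the need for it, with no gain for BACS or ESRS. The effect is minor: 40 of 672 h on treatment, and about 0.4 to 1.3 dystonia onsets trial-wide under the two assumed patterns. Those counts borrow another compound's dystonia rates, assume the timing of onset, and leave out parkinsonism.

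A reader might infer that the protocol leaves extrapyramidal symptoms untreated after the ESRS, or that efficacy results are at risk. The documents support neither. Propranolol, and possibly biperiden, stays available. PANSS is rated before ESRS in every on-treatment session and next rated 6 to 7 days later, so a benzatropine dose after the ESRS is unlikely to count as a major deviation under SAP section 3.3, Table 2. The primary analysis is not affected.

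Confidence is medium, because the intended meaning and biperiden's status cannot be settled from the text.

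**What to change.** In the benzatropine timing cell of Table 5, replace *of* with *prior to*, so that the limit covers the 8 hours before BACS and ESRS only. Apply the change to biperiden only if the original table merges the two cells; otherwise leave biperiden as it is.

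Do not add a general statement that treating extrapyramidal symptoms at or after the ESRS is not a deviation. Without a drug, dose or time limit it could excuse a dose shortly before a later BACS or ESRS, or one above the daily maximum, since every moment after Day 1 follows some ESRS. The cell change is enough.

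There is a small downside. A dose after the ESRS may precede the other same-day assessments listed in step 4 of the working. Its time should be considered when those are read, and it is already captured: "The amount and timing of each lorazepam, zolpidem, benzatropine/biperiden, or propranolol administration should be recorded for each patient in the eCRF".

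The cost is one table cell, with no change to assessments, data collection, sample size or analysis. The documents do not show whether dosing continues. If it has ended, the same one-way reading can be applied when deviations are classified at the blinded data review.
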